The following clinical claims/MNBA items as defined in the Clinical evaluation plan [3] are to be evaluated:

[REDACTED]	[REDACTED]

**Hydraulic MPK

No risks or anticipated adverse device effects (ADE) are to be assessed.

The hypothesis and endpoints are specified in Table 5.

For all hypothesis:

μ_1 is average of measurements at baseline (comparator);

μ_2 is the average of measurements at 3 week follow up (investigational device);

μ_3 is the average of measurements at 4 week follow up (comparator);

Phase I – Pre-launch

Data collected at phase I may be used to inform sample size needed for phase II if needed, as researchers will be using the same procedures as in phase I.

Table 5 Phase I Endpoints, test methods and hypotheses

	Hypothesis	Test Methods	Endpoints	Acceptance Criteria
1A1	Users rate their satisfaction in stair descent on the Rheo knee 4/Navii as no worse compared their prescribed MPK	
Self report: Modified PEQ ambulation subscale (item 13D)
 
Please rate how you felt about being able to walk down stairs when using your prosthesis/the test prosthesis?
 
1=cannot, 10=No problem
	Rating (1-10)	No worse rating compared to prescribed MPK $(89\% HDI_{low} \geq 0$ $pd > 97,0\%$ $ROPE < 2,5\%)$
1A2	Users rate their satisfaction in hill descent on the Rheo knee 4/Navii as no worse compared their prescribed MPK	
Self-Report: Modified PEQ ambulation subscale (item 14F)
 
Please rate your ability to walk down a steep hill when using your prosthesis/the test prosthesis?
 
1=cannot, 10=No problem
	Rating (1-10)	No worse rating compared to prescribed MPK $89\% HDI_{low} \geq 0$ $pd > 97,0\%$ $ROPE < 2,5\%)$
1B	Users balance confidence on the Rheo knee 4/Navii is no worse than on their prescribed MPK	
Self-Report (ABC Balance confidence scale)
 
Support question:
	ABC score (0-100%)	No worse ABC score than on prescribed MPK $89\% HDI_{low} \geq 0$ $pd > 97,0\%$ $ROPE < 2,5\%)$

		
Modified PEQ Satisfaction Question (16A)
 
Please rate how safe you have felt with your prosthesis/the test prosthesis? (1=extremely unsafe, 10=extremely safe)
		

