1C	
Users standing comfort on the Rheo knee 4/Navii is improved compared to on their prescribed MPK
	
Self-Report: PEQ item 1D
 
Please rate your comfort while standing when using your prosthesis/the test prosthesis. (1=terrible, 10=excellent)
	Rating (1-10)	
Rating of comfort improved compared to prescribed MPK
 
(89% $HDI_{low} \geq 0$ $pd > 97,0\%$ $ROPE < 2,5\%$)

Exploratory/Secondary

Phase 2 (after launch)

Clarification: More subjects may be recruited after launch of the product in order to carry out a subgroup analysis, making a technology specific comparison (hydraulic & magnetorheologic MPKs compared to Rheo knee 4/Navii). Procedures will be the same as in phase I in order to be able to combine the data from all subjects in each subgroup. Therefore, subjects will be assigned to subgroups based on their prescribed MPK at the second phase of the analysis.

Data collected at phase I may be used to inform sample size needed for phase II, as researchers will be using the same procedures as in phase I.

Table 6 Phase II – Endpoints, test methods and hypotheses

#	Hypothesis	Test Methods	Endpoints	Acceptance Criteria
2A1	Users satisfaction on functioning on the Rheo knee 4/Navii in hill/ramp descent is no worse compared to hydraulic MPKs	
Self Report: Modified PEQ ambulation subscale (item 14F)
 
Please rate your ability to walk down a steep hill when using your prosthesis/the test prosthesis?
 
1=cannot, 10=No problem
	Rating (1-10)	
No worse rating compared to prescribed hydraulic MPK
 
(89% $HDI_{low} \geq 0$ $pd > 97,0\%$ $ROPE < 2,5\%$)

2A2	Users satisfaction on functioning on the Rheo knee 4/Navii in hill/ramp descent is improved compared to Rheo Knee 3	
Self Report: Modified PEQ ambulation subscale (item 14F)
 
Please rate your ability to walk down a steep hill when using your prosthesis/the test prosthesis?
 
1=cannot, 10=No problem
	Rating (1-10)	
Improved rating compared to prescribed magnetorheologic MPK
 
(89% $HDI_{low} \geq 0$ $pd > 97,0\%$ $ROPE < 2,5\%$)

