2B1	Users satisfaction on functioning on the Rheo knee 4/Navii in stair descent is no worse compared to hydraulic MPKs	
Self report: Modified PEQ ampulation subscale (item 13D)
 
Please rate how you felt about being able to walk down stairs when using your prosthesis/the test prosthesis?
 
1=cannot, 10=No problem
	Rating (1-10)	
No worse rating compared to prescribed hydraulic MPK
 
89% $HDI_{low} \geq 0$ $pd > 97,0\%$ $ROPE < 2,5\%$)

2B2	Users satisfaction on functioning on the Rheo knee 4/Navii in stair descent is improved compared to Rheo Knee 3	Self report: Modified PEQ ambulation subscale (item 13D) Please rate how you felt about being able to walk down stairs when using your prosthesis/the test prosthesis? 1=cannot, 10=No problem	Rating (1-10)	Improved rating compared to prescribed magentorheologic MPK $(89\% HDI_{low} \geq 0$ $pd > 97,0\%$ $ROPE < 2,5\%$
-----	--	---	---------------	--

• Design of the Clinical Investigation

• General

The test will be a non-randomized single group open label prospective repeated measures (ABA) design.

Amputees are a small proportion of the general population. The population group specified in the inclusion/exclusion criteria is a further subsample of amputees. For practical reasons, i.e. to achieve statistical power, it is therefore more feasible to use within-subject comparison rather than creating study arms to compare. Furthermore, as mobile amputees generally have and use a prosthetic device for their daily activities, within-comparison is feasible comparing to the subject's previous device.

All investigational activities will be conducted at prosthetic out-patient clinics.

As stated above the primary endpoint is Satisfaction on descending stairs, see Table 5, and the secondary endpoints are satisfaction on descending ramps, balance confidence and standing comfort in that respective order of significance. In addition, there are two exploratory endpoints on mobility and balance during ambulation. See previous chapter on objectives and hypothesis and Table 5 for rationale.

Drop-outs and withdrawals may be replaced if deemed necessary to fulfil the methodological standards of the study.

Instruments for data collection will include the following:

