The design will be a non-randomized single group open label prospective repeated measures (ABA). Thereby, differences in efficacies of two classes of MPKs are investigated. For each hypothesis (1A1, 1A2, 1B, 1C), i , the population parameter for Rheo Knee 4/Navii, μ_{i1} is compared to the corresponding population parameter for other MPKs, μ_{i2} . For each research question i , the null and hypothesis is $H_{0i}: \mu_{i1} = \mu_{i2}$, and the alternative hypothesis is $H_{Ai}: \mu_{i1} \neq \mu_{i2}$. Hypotheses are investigated using a Bayesian regression framework. Evidence for H_{0i} or H_{1i} is collected using the posterior distribution of differences in efficacies for each hypothesis. Using the posterior distribution, statistical measures as the 89% high density interval (HDI), the percentage in the region of practical equivalence (% ROPE), and the probability of direction (PD) will be used to gather evidence for or against each hypothesis.

Acceptance criteria relate to the 89% HDI. An 89% HDI not covering 0 indicates a true difference between the two groups.

For trial phase II, a similar procedure will be performed and uses adjusted priors for model generation. These priors will be generated from the posterior distribution of the first trial, therefore making the prior more informative.

Using bayes theorem, the distribution of differences for each characteristic is represented by the posterior distribution and the high density interval will be used. A percentage of 89% for the HDI will be used because it was shown to be more stable than the 95% HDI. A specific significance level as in the frequentist approach is not used, although the % ROPE is related to a frequentists P value, and therefore a significance level.

For phase II, Bayesian power analysis will be performed to identify appropriate sample sizes. Sample sizes for each group that result in a power >80% are considered to be appropriate. Statistical power will be calculated using simulation studies. For any combination of sample sizes, the percentage of simulations where the minimum of the HDI will be >0 (therefore indicating a true effect (or difference) between the groups for a specific hypothesis) is equal to statistical power.

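### The primary 'no worse' hypothesis is judged by a superiority rule against zero, so a truly equal device would almost always fail it

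*Combined protocol and SAP*

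**What the plan says.** The section Design of the Clinical Investigation, General, names the primary endpoint: "As stated above the primary endpoint is Satisfaction on descending stairs, see Table 5". In Table 5 that row is 1A1, with the hypothesis "Users rate their satisfaction in stair descent on the Rheo knee 4/Navii as no worse compared their prescribed MPK" and the acceptance text "No worse rating compared to prescribed MPK". Row 1A2 (hill descent) is worded the same way. Row 1B reads "Users balance confidence on the Rheo knee 4/Navii is no worse than on their prescribed MPK". In Table 6, rows 2A1 and 2B1 claim no inferiority to hydraulic knees ("No worse rating compared to prescribed hydraulic MPK"). Phase II is optional: "More subjects may be recruited after launch of the product".

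Three rows make a different claim. Row 1C reads "Rating of comfort improved compared to prescribed MPK", and 2A2 and 2B2 claim improvement over Rheo Knee 3.

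All eight rows carry the same three thresholds: 89% HDI lower limit ≥ 0, pd > 97.0%, ROPE < 2.5%.

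Statistical design and procedures sets equality against inequality for every Phase I hypothesis, ties acceptance to the 89% HDI, and adds: "An 89% HDI not covering 0 indicates a true difference between the two groups". It defines Phase II power as the share of simulations whose HDI minimum exceeds 0. Sample size calculation gives 14 completers, power 0.9600638 and significance 0.05; the effect size is redacted.

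**The concern.** 'No worse' and 'improved' are different claims, and the tables treat them as different, yet one rule decides both. An HDI lower limit at or above 0 and a pd above 97% both ask for evidence that the new knee is better. ROPE < 2.5% asks for almost no posterior mass near equality, which is the opposite of what would support comparability. The Justification for the Design gives comparable or no worse performance on descending activities, relative to hydraulic knees, as an aim.

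The error does not create false claims: a device that passes is certainly supported as no worse. The damage lies in the other direction. An equal device is one of the cases the primary hypothesis is meant to cover, and the pre-specified rule fails it nearly every time. The posterior can still be read after a failure, but calling it 'no worse' would then need a margin, and the visible text fixes none in advance. The results are meant for marketing and regulatory documentation (Publication Policy), so a margin chosen after the data would carry little weight.

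**Working it through.** **Inputs.** Thresholds from Tables 5 and 6; n = 14, power 0.9600638 and α = 0.05 from Sample size calculation. Assumed, because not stated: a flat Phase I prior and normal paired differences (Navii minus prescribed knee). Effects are in SDs of the paired difference.

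**1. The plan's own figure.** The effect size is redacted, so N = 14 cannot be reproduced directly. Solving the noncentral-t power of a paired t-test, 1 − F(t_crit; 13, d_z√14) = 0.9600638, gives:
- one-sided (t_crit = 1.771): d_z = 0.960, with power 0.9465 at n = 13, so 14 is the smallest n reaching 0.95;
- two-sided (t_crit = 2.160): d_z = 1.075, with power 0.9443 at n = 13.

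The stated power fits a test against zero for a gain of about 1 SD. The redaction means this cannot be confirmed.

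**2. What the rule tests.** The posterior of the mean difference is a t distribution with n − 1 df, centred at the sample mean d̄ with scale s/√n. It is symmetric, so the 89% HDI leaves 5.5% in each tail. With T = d̄√n/s:
- HDI low ≥ 0 is T ≥ t(0.945, n−1), which is 1.715 at n = 14;
- pd > 97% is T > t(0.97, n−1), which is 2.060 at n = 14 and implies the HDI condition.

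**3. Equal device.** At a true difference of 0, T follows t(n−1). Failure is therefore exactly 94.5% (HDI) or 97.0% (HDI plus pd) for every n. Simulation with 400,000 trials gave 94.6%/97.0% at n = 14 and 94.5%/97.0% at n = 200.

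**4. Adding ROPE < 2.5%.** This can only raise failure. No half-width is visible, so these are illustrations at n = 14: about 98.3–98.7% at ±0.1 SD and 99.4–99.6% at ±0.2 SD. At ±0.1 SD it rises to 99.6% at n = 50.

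**5. Slightly better device, n = 14.** Pass probability is 1 − F(t_crit; 13, δ√14).

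| True gain δ | HDI | HDI + pd |
|---|---|---|
| 0.25 SD | 24% | 16% |
| 0.5 SD | 57% | 45% |
| 1.0 SD | 97% | 94% |

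An 80% pass rate needs a true gain of 0.69 SD (HDI) or 0.78 SD (HDI plus pd).

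**6. Sensitivity, equal device, n = 14.**
- Normal priors with mean 0, +0.25 or +0.5 SD and prior SD 0.5, 1 or 2 (known SD): failure about 90–96.5% (HDI) or 94.5–98.3% (HDI plus pd).
- Integer 1–10 ratings (assumed means 6, 7.5 or 9, SD 2, correlation 0.5): 93.6–94.6% or 96.3–97.0%.

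**7. A margin rule, HDI low > −M, n = 14.** Same formula with noncentrality (δ + M)√14:

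| M (SD) | δ = 0 | δ = +0.1 SD | δ = +0.25 SD |
|---|---|---|---|
| 0.25 | 24% | 36% | 57% |
| 0.5 | 57% | 70% | 86% |
| 0.75 | 86% | 92% | 97% |
| 1.0 | 97% | 99% | 99.8% |

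A device worse by exactly M passes 5.5% of the time.

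**The case against.** Several points can be made for the plan.

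- **A strict zero margin.** HDI low ≥ 0 can be read as high posterior probability that the new knee is not worse at all. That is coherent, but it explains neither the ROPE criterion nor the use of the same rule for 'improved'.
- **The prior.** An informative, optimistic Phase I prior would change the figures. A prior worth 25 subjects, the size of the pilot, has an SD of about 1/√25 = 0.2. At n = 14 and a true difference of 0, failure on the HDI is then 99.6%, 84.1% or 25.0% for prior means of 0, +0.25 or +0.5 SD. The arithmetic is right, and it shows that the percentages depend on the prior. But nothing in the documents states such a prior, and the pilot's comparator was earlier Rheo versions. The Phase II prior is also described as the more informative one.
- **Which rule applies.** HDI plus pd without ROPE is not a rule the plan states. The plan does not say whether the three criteria are joint. On the HDI alone failure is 94.5%; each added criterion can only raise it.
- **Redaction.** Table 4 and the sample-size inputs could contain a margin. The acceptance criteria are legible, however, and use 0, so a margin elsewhere would contradict them.
- **Conservatism.** No false claim follows from a pass, and clear inferiority remains visible: under the flat prior at n = 14, the HDI lies wholly below 0 in 24%, 57%, 86% and 97% of trials at −0.25, −0.5, −0.75 and −1.0 SD. This stands. It limits the harm but does not make the primary criterion answer its own question.

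**Conclusion.** The concern holds. Five rows, including the primary one, claim 'no worse' and are judged by thresholds identical to those for 'improved'. That follows from the legible text and needs no assumption. Under a flat prior with normal paired differences, an equal device fails 94.5% (HDI) or 97.0% (HDI plus pd), and enrolling more subjects does not help. The figures apply to Phase I only, because Phase II takes its priors from the Phase I posterior. The wording conflict does carry over to 2A1 and 2B1, and the Phase II power definition would size those rows for superiority as well. This must be fixed before data are seen, since a margin chosen later would not be credible.

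**What to change.** Choose one option before any data are seen.

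**(a) Match the claim to the rule.** Reword 1A1, 1A2, 1B, 2A1 and 2B1 as improvement claims. The cost is text edits to Tables 5 and 6, the Justification for the Design and the comparability statements under Anticipated clinical benefits, plus a check against the redacted claims in Table 4. The sample size would stay as it is if it was derived for superiority. At the back-solved gains of 0.96 or 1.08 SD the rule passes 96% or 99% (HDI), or 93% or 97% (HDI plus pd). The drawback is a stronger claim that an equal device still almost always fails.

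**(b) Match the rule to the claim.**
- Pre-specify and justify a margin M for each scale (1–10 ratings; ABC 0–100%).
- Judge the five rows by 89% HDI low of (Navii − prescribed knee) > −M.
- Drop pd against zero and ROPE < 2.5% from those rows.
- Restate their hypotheses as difference ≤ −M against difference > −M.
- Use HDI minimum > −M in the Phase II power definition for 2A1 and 2B1.
- State the power of 14 completers for the chosen M and the assumed true difference.

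The cost is edits to both tables and the statistical and sample-size text, a defended margin per scale, and possibly more subjects: M = 0.5 SD gives 57% power at a true difference of 0 and 86% at +0.25 SD.

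**Under either option,** keep the current thresholds for 1C, 2A2 and 2B2, and say whether the three criteria must hold jointly. State the Phase I prior. Fix the direction of the difference: Objectives and Hypotheses labels the comparator as the first mean, while Statistical design and procedures labels the Navii as the first. Check the pointer in Sample size calculation that sends the reader to Table 4 for the pass/fail criteria.

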A subject can withdraw from participation at any time, at his/her discretion, and this will not have any consequences for the participant's treatment. In such cases a report stating reasons for discontinuation of the participant shall be prepared by the LPI. No further investigational procedures concerning the subject will be conducted, except for a statement explaining the reason for withdrawal, including but not limited to: interacting or interviewing the subject in order to obtain data on him/her; obtaining additional private information on the subject by either observing the subject or collecting or receiving such information from any source.

The LPI can withdraw the participant from the trial at any time. The reasons shall be documented. There are no pre-specified criteria for discontinuation of participants from the trial. The discontinuation of participants in the trial may result in replacement with new participants. If withdrawal is due to problems related to the investigational device the participant will be asked for permission to follow the status/condition outside the clinical investigation. The follow-up will be individualized.

Subjects will be enrolled at the clinic, the investigational site that they were contacted from.

The total time period required to implement the clinical investigation (**phase I**) is expected to be **8 weeks**. Each individual subject is expected to participate in the clinical investigation for **5 weeks**. The estimated time needed to include this number (enrolment period) is **2 weeks**.

The estimated time period needed to implement **phase II** will depend on the number of subjects needed for that phase, but it is anticipated it will take around **8-10 weeks**.

14 subjects are required to finish the protocol for statistical data analysis, as specified in chapter 10.2 Sample size calculation.

- **Procedures**

- i) Recruitment**

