The second visit will be at three weeks after visit 1. During this visit subjects will complete the same functional tests and questionnaires as at visit 1 (excluding background information) on the investigational device, with the addition of a usability questionnaire. They will then be fitted back to their prescribed device.

The third visit will be three weeks later. During this visit subjects will complete the same functional tests and questionnaires as at visit 2 (excluding usability questionnaire) on their prescribed device, as well as completing a qualitative interview on their experiences with both microprocessor knee devices.

- iii) Measurements and data collection**

The same questionnaires, consisting of three valid instruments (PEQ questions, PLUS-M and ABC), will be used and filled in at three separate points in time. Background information will be collected at baseline only, usability questionnaire at visit 2 only and qualitative interview at visit 3 only. An activity report will be generated from the investigational device at visit 2 and an activity report from subjects prescribed device at visit 3, if applicable.

Table 8 Visit schedule and procedures

	Recruitment phase: 2-4 weeks prior to baseline	Subject visit 1: BL prescribed device	Subject visit 2: FU RK 4/Navii	Subject visit 3: FU Prescribed device
Potential subjects identified, fitting inclusion/exclusion criteria, by LPI from customer database		X		

LPI calls potential subjects and screens by telephone	X			
Subject signs ICF	X			
Subject fills in background information questionnaire (PIS)	X			
Subject fills in validated questionnaire (PEQ, PLUS-M, ABC)	X	X	X	
Subject fitted with investigational device and receives training according to training protocol	X			
Subject fills in usability questionnaire for the investigational device		X		
Subject is fitted back to their prescribed prosthesis		X		
LPI prints out activity report from the investigational device/ prescribed device		X	X	
Subject completes qualitative interview			X	
End of study				X

For each subject there are **three** scheduled **visits** to the study site and **questionnaires and functional tests** are administrated **three** times during the course of the study.

- Compensation

iv) Subject

- Responsibilities

Sponsor Principal Investigator (PI)

- Identify sites
- Collect Data
- Investigate possible vigilance cases/SAEs
- Monitor trial
- Technical support

Monitor

- Train site staff on study procedures
- Monitor trial

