Any deviations from the statistical plan provided in this protocol will have to be approved by the sponsor and the reasons for the deviation reported in the clinical investigational report. Drop-outs and withdrawn participants will be included in the data analysis for the procedures that they completed. They will be grouped together and compared to the group that finished the protocol. Any statistical differences of the two groups will be reported. If the participants have not provided any data, they will not be included in the data analysis. No particular information will be excluded from the statistical analysis and tests, as described above.

• Amendments and Deviations from the Protocol (CIP)

• Amendments

Any amendments to this protocol must be first approved by the sponsor and PI, and then be evaluated by the overseeing IRB and, where appropriate regulatory authorities, before being implemented.

For non-substantial changes (e.g. minor logistical or administrative changes, change of monitor(s), telephone numbers, renewal of insurance) not affecting the rights, safety and well-being of human subjects or not related to the clinical investigation objectives or endpoints, a simple notification to the IRB and, where appropriate, regulatory authorities can be sufficient.

• Deviations

Investigators are not allowed to deviate from this protocol without a formal approval from the IRB, if the deviation affects subject's rights, safety and wellbeing, or the scientific integrity of the clinical investigation. Any such deviation from the protocol is to be documented in detail and the report sent to the IRB.

Under emergency circumstances, deviations from the protocol to protect the rights, safety and well-being of human subjects may proceed without prior approval of the sponsor and the IRB. Such deviations shall be documented and reported to the sponsor and the IRB as soon as possible.

Investigators can request for an approval from the sponsor for a deviation if the deviation does not affect subject's rights, safety and wellbeing, or the scientific integrity of the clinical investigation.

In case of a deviation from this protocol taking place without prior approval from the sponsor, and IRB as applicable, it shall be reported to the sponsor within 24 hours of LPI knowledge of the deviation. The LPI responsible for the deviation is to send a report to the sponsor no later than five days after the deviation was reported. The report shall include:

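### A subject who gives up the investigational knee before visit 2 leaves no rating of it, so device-related stops bias the satisfaction result in the device's favour, and nothing in the plan corrects this

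*Combined protocol and SAP*

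**What the plan says.** The section Design of the Clinical Investigation, General, names the outcome: "As stated above the primary endpoint is Satisfaction on descending stairs". It is item 13D, a 1 to 10 self-rating (Table 5). The only scheduled rating on the investigational knee is at visit 2, three weeks after fitting (Procedures, Test procedure): "During this visit subjects will complete the same functional tests and questionnaires as at visit 1 (excluding background information) on the investigational device". The weekly telephone calls check for problems; no rating is scheduled in them.

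For subjects who leave, the Subjects section says: "No further investigational procedures concerning the subject will be conducted, except for a statement explaining the reason for withdrawal". Where the device is the cause, "the participant will be asked for permission to follow the status/condition outside the clinical investigation". Replacement is allowed in the General section ("Drop-outs and withdrawals may be replaced if deemed necessary to fulfil the methodological standards of the study") and again under Subjects ("The discontinuation of participants in the trial may result in replacement with new participants"). Neither sentence depends on the reason for leaving.

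The target is that "14 subjects are required to finish the protocol for statistical data analysis". Sample size calculation recruits 17 to allow for 20% drop-out. Additional statistical matters states: "Drop-outs and withdrawn participants will be included in the data analysis for the procedures that they completed". It also plans to compare those who left with those who finished. It specifies no imputation, unfavourable score or sensitivity analysis for a missing device rating.

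**The concern.** The outcome is satisfaction with a device, in an open-label study with one group. Disliking the knee is a plausible reason to stop using it, and under these rules stopping removes the unfavourable score. A subject who leaves before visit 2 has at most a baseline rating of the prescribed knee. There is then no within-subject difference, and the comparison of leavers with completers has no device rating to compare. No concurrent arm exists in which similar losses might offset the effect.

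At stake are the no-worse claims (1A1, 1A2, 1B) and the improvement claim (1C). Statistical design and procedures takes the Phase II priors from the Phase I posterior, so a bias in Phase I would carry into the later subgroup claims.

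**Working it through.** **The plan's own figure.** 14 × 1.2 = 16.8, rounded up to 17, which reproduces the recruitment number. Going from 17 to 14 is a loss of 3, or 3/17 = 17.6%. The plan therefore already expects about three losses, with no replacement needed.

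**Size of the shift.** If k of 17 fitted subjects leave without a device rating, the completers' mean differs from the mean of all fitted subjects by

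(k/17) × (completers' mean difference − leavers' mean difference).

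With k = 3, each point by which leavers would have scored lower than completers adds 3/17 = 0.18 points to the estimate.

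**Chance of passing.** Inputs from the plan are 17 subjects, 14 completers, and the Table 5 criteria (89% HDI lower limit at or above 0, probability of direction, pd, above 97.0%, ROPE below 2.5%). The following are assumptions:
- Within-subject differences (device minus prescribed knee) are normal. Results are in SD units because the effect size and SD are blacked out.
- With a flat prior, pd above 97% equals a one-sided t criterion at 0.03. This is stricter than the HDI condition, which corresponds to 0.055.
- All 17 are fitted and 3 leave before visit 2. Leaving depends on the unseen difference through a correlation of 0, 0.3, 0.5 or 0.8. The worst case is that the three lowest scorers leave.
- ROPE is left out at first, because its width is not given.

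Simulated results (200,000 or more trials per row), chance of pd above 97%:

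| Loss | Shift (SD) | True difference 0 | True difference −0.2 SD |
|---|---|---|---|
| None, 17 analysed | 0 | 3% | 0.4% |
| 3 lost, correlation 0 | 0 | 3% | 0.5% |
| 3 lost, correlation 0.3 | 0.09 | 6% | 1% |
| 3 lost, correlation 0.5 | 0.15 | 10% | 2% |
| 3 lost, correlation 0.8 | 0.24 | 19% | 5% |
| 3 lost, worst case | 0.30 | 30% | 10% |

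In the worst case the observed SD also falls, from 0.98 to 0.78. The narrower spread adds to the effect of the shift.

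**Adding the ROPE condition** at an assumed half-width of 0.1 or 0.2 SD:
- True difference 0: 18% or 9% in the worst case, against 1% or 0.3% with no loss.
- True difference −0.2 SD: 5% or 2% in the worst case.

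**Which column applies.** At a true difference of zero, passing is an error only for an improvement claim such as 1C. For the primary no-worse claim the device must truly be worse, so the −0.2 SD column applies. At −0.3 SD the worst case is about 5%, and at −0.5 SD about 0.7%.

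**Replacement.** Replacing leavers until 17 complete gives shifts of 0.10, 0.16 and 0.25 SD at correlations 0.3, 0.5 and 0.8, and 0.32 SD in the worst case. These are nearly the shifts without replacement. At a true difference of zero, the worst-case chance of passing goes from 30% to 35%, mainly because more completers are analysed.

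**The case against.** A reader might infer that the replacement rule is what removes dissatisfied users. The documents do not support that. The missing rating creates the shift, and it is present with nobody replaced. Nor does the text say that replacement continues until 14 finish, or who decides.

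A reader might also take the rise from 3% to 30% as the false-pass rate of the primary endpoint. It is not. It is a worst case on pd alone, at a true difference of zero, where a no-worse verdict is correct. Requiring the HDI lower limit to reach zero already protects the no-worse claims considerably.

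Other points in the plan's favour:
- Subjects go home only once they feel comfortable and safe on the knee. They are telephoned weekly and can be seen at the site if problems arise, so early abandonment may be rare.
- Reasons for withdrawal are documented, so device-related losses would be visible.
- The regression model is not specified, and a mixed model could use baseline-only subjects.
- A subject who leaves between visits 2 and 3 already has a device rating.

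All of these stand. They limit the likely size or show that a loss occurred. None supplies the missing rating, and a mixed model does not recover scores that are missing because of their own value.

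**Conclusion.** The concern holds as a gap in data collection and analysis. Under the written rules, a subject who stops the knee early through dissatisfaction drops out of the comparison, and the completers' estimate is then biased towards the device. The direction is certain only for stops of that kind; losses unrelated to satisfaction cause no shift. The actual size cannot be known from the documents.

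With the plan's own expected loss of three, even modest dependence (correlation 0.3 to 0.5) doubles or triples the chance of wrongly supporting an improvement claim. The primary no-worse claim is less exposed: the error stays at or below about 10% at a true deficit of 0.2 SD, and lower still if the ROPE condition binds. These figures rest on normal differences, a flat prior and the assumed ROPE widths. It is worth correcting because the remedy is cheap, not because the result is shown to be unsound.

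**What to change.** 1. **Subjects section.** Amend the bar on procedures after withdrawal so that a subject who stops the device early is asked, with consent, to complete the visit-2 questionnaires when the knee is exchanged back. Record the time on the device.
2. **Additional statistical matters.** Make all fitted subjects the analysis set. Pre-specify a sensitivity analysis for device-related stops that uses the exit rating, or an unfavourable rating where none exists. Report whether each Table 5 verdict still holds.
3. **General and Subjects sections.** If subjects are replaced, keep the replaced subjects in that analysis set and report their number and reasons.

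The cost is wording in three places and one questionnaire. The prescribed prosthesis is held at the site, so most subjects who stop would return there to exchange knees. There are two drawbacks: an exit rating reflects less than three weeks of use, and the unfavourable score is one choice among several. Both belong in a sensitivity analysis and not in the primary analysis.
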